Study Schema: Drugs / Doses / Length of Treatment)	
 • Ipilimumab 3mg/Kg iv q 3 weeks for 4 cycles • WBRT 30 Gy in 10 fractions (or radiobiological equivalent schedule, after Sponsor approval), starting between C1D2 and C2D1
Study Objectives: Primary: Secondary:	
Primary Objective
 
 • Efficacy - Primary endpoint: 1-year survival rate 
Secondary Objectives
 
 • Efficacy – Endpoints: 
 ○ Progression-Free survival-PFS (median, 6-month PFS rate) 
 ▪ Intracranial PFS (median, 6-month PFS rate)

	
 ▪ Extracranial PFS (median, 6-month PFS rate) 
 ○ Overall survival (median) ○ Response rate: (global, intracranial, extracranial) (“Immune-related response criteria”) ● Safety: Adverse Event rates ● Feasibility: dose delays/reductions, treatment exposure
Study Design:	Multicenter, single arm, phase 2 clinical study on the combination of radiation therapy and ipilimumab
Accrual Goal: (Total number of patients)	56 patients treated 66 included
Accrual Rate: (Number of patients expected per month)	3 to 4 patients per month
FPFV: LPFV: Follow Up: (dd-mm-yy)	03/2014 10/2015 10/2016
Correlative Studies: (PK/PD, etc.)	
Exploratory Objectives.
 
 ○ Potential baseline predictors of efficacy (in tumor tissue and peripheral blood) 
Potential early surrogates for response: inpatient variation of quantitative apparent diffusion coefficients of serial diffusion-weighted magnetic resonance imaging

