- In addition, in all ipilimumab trials examined to date, mean Absolute Lymphocyte Count (ALC) increased after ipilimumab treatment throughout the 12-week induction-dosing period, in a dose-dependent manner. In an analysis of ipilimumab at 0.3, 3, or 10 mg/kg in melanoma studies CA184007, CA184008, and CA184022 combined, the rate of change in ALC after ipilimumab treatment was significantly associated with dose (p = 0.0003), with the largest rate at 10 mg/kg ipilimumab. Moreover, the rate of change in ALC over the first half of the induction-dosing period was significantly associated with clinical activity in these studies (p = 0.009), where clinical activity was defined as CR, PR, or prolonged SD (ie, SD lasting at least 6 months from first dose). Although these analyses alone could not determine whether the rate of change in ALC was specifically associated with clinical activity in response to ipilimumab treatment, as opposed to being generally prognostic, these results do suggest a potential benefit to higher rates of ALC increase after ipilimumab treatment. Among the 3 doses evaluated, 10 mg/kg ipilimumab led to the greatest such rates.
- In the 3 primary studies conducted in advanced melanoma (CA184007, CA184008, and CA184022), subjects treated with 10 mg/kg during the induction period had the highest response, disease control rates, median OS as well as 1-year and 2-year survival rates compared to other doses. The CA184022 data are summarized in Table 10.

Table 10: Summary of Phase 2 Response Data in Melanoma (CA184022)

	10 mg/kg (n = 72)	3 mg/kg (n = 72)	0.3 mg/kg (n = 73)
BORR (mWHO) – %	11.1	4.2	0
(95% CI)	(4.9 - 20.7)	(0.9 - 11.7)	(0.0 - 4.9)
DCR (mWHO) – %	29.2	26.4	13.7
(95% CI)	(19.0 - 41.1)	(16.7 - 38.1)	(6.8 - 23.8)
Survival rate at 1 year - %	48.64	39.32	39.58
% , 95% CI	(36.84, 60.36)	(27.97, 50.87)	(28.20, 51.19)

GRAY-B Study (GEM 1202). V1.0 (28 Nov 2013)

Survival rate at 2 year - %	29.81	24.20	18.43
%, 95% CI	(19.13, 41.14)	(14.42, 34.75)	(9.62, 28.22)
Overall median survival	11.43	8.74	8.57
95%CI (months)	(6.90, 16.10)	(6.87, 12.12)	(7.69, 12.71)

Finally, the dose and schedule in study CA184156 is the one that was evaluated in the signal finding study CA184041, with an acceptable safety profile and improvement of irPFS and OS.

Treatment with ipilimumab has demonstrated clinically important and durable tumor responses in several malignancies including melanoma, prostate cancer, and renal cell carcinoma.

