2.2 Secondary Objectives

- Efficacy – Endpoints:
 - Progression-Free survival-PFS (median, 6-month PFS rate)
 - Intracranial PFS (median, 6-month PFS rate)
 - Extracranial PFS (median, 6-month PFS rate)
 - Overall survival (median)
 - Response rate: (global, intracranial, extracranial) (“Immune-related response criteria”)
- Safety: Adverse Event rates
- Feasibility: dose delays/reductions, treatment exposure

2.3. Exploratory Objectives.

- Potential baseline predictors of efficacy (in tumour tissue and peripheral blood – see 6.4.3.)
- Potential early surrogates for response: inpatient variation of quantitative apparent diffusion coefficients of serial diffusion-weighted magnetic resonance imaging

⁶⁸ Hodi FS, O'Day SJ, McDermott DF, et al. Improved survival with ipilimumab in patients with metastatic melanoma. *N Engl J Med.* 2010 Aug 19;363(8):711-23.

⁶⁹ http://www.ema.europa.eu/docs/en_GB/document_library/EPAR_-_Product_Information/human/002213/WC500109299.pdf

3 **STUDY DESIGN**

This is a non-controlled, single stage, multicenter phase 2 clinical study. A total of 56 evaluable patients will be treated in this study.

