- 8) Therapy with any of the following: IL-2, interferon, or other non-study immunotherapy regimens; cytotoxic chemotherapy; immunosuppressive agents; target molecular inhibitors (BRAF, MEK, KIT); or chronic use of systemic corticosteroids (used for the management of non-cancer related illnesses), either concomitantly or during the last 3 weeks prior to the beginning of the treatment.
- 9) Any experimental therapy administered in the past 30 days prior to the beginning of the treatment.
- 10) Any non-oncology vaccine therapy used for the prevention of infectious diseases (for up to 4 weeks prior to or after any dose of blinded study drug)
- 11) Women of childbearing potential (WOCBP), as defined above in “Inclusion criteria”, who:
 - a. are unwilling or unable to use an acceptable method of contraception to avoid pregnancy for their entire study period and for at least 26 weeks after cessation of study drug, or
 - b. have a positive pregnancy test at baseline, or
 - c. are pregnant or breastfeeding.
- 12) Prisoners or subjects who are compulsorily detained (involuntarily incarcerated) for treatment of either a psychiatric or physical (eg, infectious) illness.
- 13) Any other general, medical or psychological conditions which in the opinion of the investigator will make the administration of ipilimumab hazardous, or that would preclude appropriate informed consent or compliance with the protocol, or obscure the interpretation of eventual AEs.

4.3 **Data Safety Monitoring Plan**

A Data Safety Monitoring Committee (DSMC) will be designated prior to the initiation of the study, and chaired by the coordinating principal investigator. The DSMC will meet approximately every 4 months to ensure that subject safety is carefully monitored. The DSMC might also be consulted on an *ad-hoc* basis should a safety signal emerge, and may also convene an *ad-hoc* meeting on its own initiative. Following the review, the DSMC will recommend continuation, modification, or discontinuation of the study based on observed toxicities.

The DSMC will have access to reports of study data including analyses addressing population characteristics, dosing, safety, and efficacy updated as available prior to each of its meetings.

5. **STUDY THERAPY**

5.1. **Ipilimumab**

5.1.1. **Dose Calculations**

Each patient will receive ipilimumab 3 mg/Kg every 3 weeks, for a total of 4 administration. Infusions should be given over 90 minutes (not bolus or IV push).

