The aim of this optional study is to determine whether a correlation between the proposed biomarkers and disease behavior (progression, overall survival, treatment response) exist in patients with melanoma metastatic to the brain, that have specifically consented for the participation in this part of the study.

The present biomarker plan proposes assessment of such biomarkers to investigate their associations with immune-mediated adverse events when ipilimumab is administered with radiation therapy:

- To evaluate tumor biomarkers pathways by IHC and their correlation with prognosis as well as their role as predictive factors to treatment with ipilimumab+radiotherapy in 29 patients participating on GEM 12-02 clinical trial.
- To evaluate serum levels of several cytoquines (by means of cytoquines panel) at baseline, and before each ipilimumab administration (expected 4-5 samples per patient, 29 patients).
- To evaluate Peripheral Blood Mononuclear Cells (PBMCs), with true counts for absolute numbers and percentage at baseline, and before each ipilimumab administration (expected 4-5 samples per patient, 29 patients).

6.4.3.b Biomarker Measures

- ALC will be assessed as a part of standard hematology panel.
- CRP will be obtained as a component of the serum chemistry lab test.
- Tumor Samples: at least 29 tumor samples (biopsies) will be collected and histology and IHC will be carried out to evaluate a panel of biomarkers that includes: CD3, CD4, CD8, CD31, PD-1, PD-L1, CD45RO, CD68, NK, DC, CD80, CD86, ICAM, VCAM, HLA-A,B,C, HLA-DR, PTEN.
- Serum Samples will be evaluated in at least 29 patients at 4-5 timepoints (116 refrigerated serum samples). For each sample, 10 ml of serum will be collected and a cytokine panel will be carried out, including:

Cytokines			
IFN- γ	TNF- α	IL-1 β	IL-2
IL-4	IL-6	IL-7	IL-8

IL-10	IL-12	IL-15	IL-17
Adhesion molecules			
sICAM-1	sVCAM-1	sCD25	

- Peripheral Blood immune cells will be evaluated in at least 29 patients at 4-5 timepoints (116 refrigerated peripheral blood samples). For each sample, 10 ml of heparin blood will be collected for flow cytometry to evaluate a panel of cells that include:

T cells			
CD3	CD4	CD8	CD56
CD45RA	CD45RO	CD62L	LFA-1 (activated conformation)
NK cells			
NKp46	CD16	CD56	
T reg			
CD4	CD25	FoxP3	
MDSC			
CD14	CD15	CD33	HLA-DR
DC			
BDCA-1	BDCA-2	BDCA-3	
T cell activation (with PMA + ionomycin)			
CD69	CD25	IFN-	IL-4
IL-17	LFA-1(active conformation)		

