9.4.5 Exploratory Analyses

Two types of ALC analyses will be done: pharmacodynamic and predictive. Both analyses will include all treated subjects with known date of first dose of ipilimumab. Pharmacodynamic analyses will examine the patterns of change in ALC over time, and how these patterns might differ between treatment arms. Predictive analyses will examine potential relationships between ALC and measures of response such as overall survival.

The proposed biomarker study includes analysis of tumor tissue at diagnosis and serum/peripheral blood at different phases within the treatment schedule. All analysed parameters will be correlated with progression-free survival (PFS), overall survival and histopathological parameters.

For the statistical analysis, it will be used binary variables, reflecting the positivity status of the measures (yes or no; presence/absence). Association with histopathological parameters. The significance level will be set at 5%. To study the impact of the histological, immunohistochemical and molecular factors on progression-free survival (PFS) and overall survival (OS), the Kaplan-Meier proportional risk test (log rank) will be used. Evidence of the relative risk for each patient will be also provided by means of a Cox proportional hazards model using stepwise selection to identify the independent predictors of poor outcome.

For the kinetic profile of the serum/blood biomarkers, each variable will be considered as continuous. A correlation at different points of the treatment schedule will be considered and the slope value will be used in order to distinguish those cases with no change, negative or positive trend. The threshold will be calculated after considering the behavior of the whole series.

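### Protocol 9.4.5 plans an ALC comparison between arms that a single-arm trial does not have, and codes measured biomarkers as yes/no with no cut-off

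*Protocol*

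**What the plan says.** **Design.** Protocol section 3 states: "This is a non-controlled, single stage, multicenter phase 2 clinical study". The synopsis agrees: "Multicenter, single arm, phase 2 clinical study on the combination of radiation therapy and ipilimumab". Protocol 5.1.1 gives one regimen: "Each patient will receive ipilimumab 3 mg/Kg every 3 weeks, for a total of 4 administration".

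**ALC.** Protocol 9.4.5 plans two ALC analyses in all treated subjects. The pharmacodynamic one looks at change over time and at "how these patterns might differ between treatment arms". The one called predictive relates ALC to outcome measures such as OS; it needs no arms and is not said to be binary.

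**Other biomarkers.** Protocol 6.4.3 collects quantitative data, for example: "To evaluate Peripheral Blood Mononuclear Cells (PBMCs), with true counts for absolute numbers and percentage at baseline". It also lists a serum cytokine panel and a tissue immunohistochemistry (IHC) panel. For relating the analysed parameters to PFS, OS and histopathology, 9.4.5 says "it will be used binary variables, reflecting the positivity status of the measures (yes or no; presence/absence", followed by log-rank tests and a stepwise Cox model at the 5% level. No cut-off is given for any marker.

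**Kinetics.** The next paragraph of 9.4.5 treats the serial serum and blood variables as continuous, then sorts their slopes into flat, falling or rising: "The threshold will be calculated after considering the behavior of the whole series".

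**SAP.** The sections available (1.2 to 2.2) contain no biomarker section that defines positivity. Tables 22 and 32 do list CRP as a value without categories and the neutrophil/lymphocyte ratio as quantitative.

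**The concern.** Two things in 9.4.5 do not fit the rest of the protocol. One clause asks for a comparison that the design cannot supply. The coding rule turns measurements taken on a numerical scale into yes/no variables, without naming the markers covered or saying what counts as positive.

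At stake is the exploratory objective on baseline predictors of efficacy. For tissue, cytokines and flow cytometry it rests on a planned minimum of 29 patients. In a sample of that size, a loss of information from dichotomising is costly. An unspecified cut also leaves a choice to be made after the data are seen, and its result then enters a stepwise model. The primary endpoint is not involved.

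**Working it through.** **1. Arm contrast.** Inputs: 1 arm (synopsis; section 3) and 1 ipilimumab regimen (5.1.1). The number of pairwise contrasts among k groups is k(k − 1)/2; with k = 1 this is 0. There is no dose group that could stand in for an arm. Change over time within patients needs no second group and remains available.

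**2. The plan's own figure.** Section 9.4.5 states no size or power. Section 6.4.3 states 116 serum and 116 blood samples: 29 patients × 4 time points = 116, which reproduces the lower end of the planned 4 to 5 time points (29 × 5 = 145).

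**3. What yes/no coding does to a log-rank or Cox comparison.** With D deaths and a share a of patients coded positive, information is approximately D × a × (1 − a). The hazard ratio detectable with 80% power at two-sided 5% is exp[(1.960 + 0.842)/√(D·a·(1 − a))]. Assumption: 20 to 29 deaths among 29 patients. Section 9.4.5 does not say whether its 5% is one- or two-sided.

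| Split of 29 | Information, D = 20 | Detectable HR | Information, D = 29 | Detectable HR |
|---|---|---|---|---|
| All positive (a = 1) | 0 | none exists | 0 | none exists |
| 28 to 1 (a = 28/29) | 0.666 | 31.0 | 0.966 | 17.3 |
| Even (a = 0.5) | 5.00 | 3.5 | 7.25 | 2.8 |

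In a trial run with a constant covariate in 29 patients, the log-rank had no second group and the Cox information matrix was singular. Once a cut-off splits the sample, the binary comparison can be formed, but only large effects are detectable.

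**4. Loss against continuous analysis.** Simulation assumptions, none taken from the documents except n = 29: exponential survival with median 7 months, censoring at 18 to 36 months, a normal marker with log-linear hazard, 4000 runs, 5% level. It was run twice independently.

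| HR per SD | Continuous | Median split |
|---|---|---|
| 1.6 | 60.5% and 59% | 42.2% and 41% |
| 1.8 | 75.1% and 76% | 54.2% and 54% |

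The Monte Carlo standard error near 60% is √(0.6 × 0.4/4000) = 0.8 percentage points, so the two runs agree. With no effect, the continuous test rejected in 5.3% of runs and the outcome-blind median split in 5.7%, so the comparison is close to like for like. At HR 1.6 the loss is about 18 percentage points.

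**5. Consistency with the SAP.** SAP Tables 22 and 32 enter CRP and the neutrophil/lymphocyte ratio as quantities in logistic models of 1-year OS and 6-month PFS (the ratio also appears cut at 3). Continuous handling of blood markers is therefore already part of the plan; 9.4.5 does not extend it to the biomarker panel.

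**The case against.** **The arm clause is a trailing phrase.** The same sentence already plans ALC change over time, and no decision depends on the contrast. This stands: the cost is one void clause. It is still an analysis that cannot be delivered.

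**The binary rule may be meant for tissue.** The log-rank sentence names histological, immunohistochemical and molecular factors. Yes/no coding can suit IHC markers such as PD-L1 or PTEN, and the following paragraph keeps serial blood values continuous. This stands in part. The coding rule itself follows a statement covering all analysed parameters, and only the kinetic profile is exempted, so baseline counts and cytokine levels are left under it or left undefined.

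**Stronger readings that the documents do not support.**

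- A reader might infer that the marker analyses as a whole cannot be formed because the variables are constant. That requires taking presence in the literal sense, extending the rule to circulating cells, and knowing from outside the documents that every patient has them. If positivity means above a cut-off, the comparison exists.
- A reader might infer a false-positive rate of about 31% from data-driven cuts. The two simulations gave 30.6% and 32%, but only when the cut is chosen to maximise the association with outcome. The threshold in 9.4.5 concerns marker slopes, and outcome is not mentioned.
- A reader might infer that the whole exploratory objective rests on 29 patients. ALC is analysed in all treated subjects, and CRP is a routine laboratory test.
- A reader might object to the label predictive. One arm indeed cannot separate prediction from prognosis, and Protocol 1.3.5.d says of earlier ALC data that they could not show a treatment-specific link "as opposed to being generally prognostic". But 9.4.5 describes this analysis only as relationships between ALC and outcome, so relabelling is a matter of wording.

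**The simulation favours continuous coding.** A normal marker with log-linear hazard is its best case. This stands: a marker with a true threshold effect would lose less.

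**Conclusion.** The point holds in two parts. First, the between-arm ALC contrast cannot be made; this follows from the design alone. Second, 9.4.5 applies yes/no coding to biomarker measures without limiting it to suitable markers and without a cut-off, although the underlying data are counts, percentages and levels. The result is a possible constant covariate on the literal reading, or lost information and an open choice of cut on the other.

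The size of the second part is an illustration: at 29 patients and HR 1.6 per SD, power of about 60% falls to about 42% with a median split, under the assumed survival, censoring, normality and log-linearity. The documents do not support saying that no biomarker comparison can be formed, or that error rates are inflated to a particular figure. This should be corrected because a better method is available from data already planned. It does not touch the primary analysis.

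**What to change.** Amend Protocol 9.4.5:

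1. Delete the between-arm clause and keep within-patient ALC change over time. It can optionally be described by corticosteroid use at baseline or cycle 1, which SAP Table 7 already tabulates.
2. Analyse quantitative baseline blood and cytokine markers, and IHC markers recorded as a score, as continuous variables: log-transformed where skewed, with a Cox hazard ratio per SD. Keep yes/no coding only for markers that are truly positive or negative in a material share of patients, list those markers, and define positivity for each.
3. Set any cut-off, including the slope threshold, without reference to outcome, and say so.

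**Cost.** Wording only, with no new data or visits. The downside is that Kaplan-Meier curves by marker become illustrative and are no longer the main test.

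### The cut that sorts biomarker slopes into negative, no change and positive is set after the data are seen, with no rule that keeps PFS and OS out of the choice

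*Protocol*

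**What the plan says.** Protocol section 9.4.5 starts the kinetic analysis on a continuous scale: "For the kinetic profile of the serum/blood biomarkers, each variable will be considered as continuous". It then groups the patients: "the slope value will be used in order to distinguish those cases with no change, negative or positive trend". The cut between groups is left until the data are in: "The threshold will be calculated after considering the behavior of the whole series".

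Earlier in the same section stands the general aim, "All analysed parameters will be correlated with progression-free survival (PFS), overall survival and histopathological parameters", and a level for the tests: "The significance level will be set at 5" per cent. The log-rank test is named there for histological, immunohistochemical and molecular factors; no test is named for the slope groups.

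Section 6.4.3 plans serum and blood-cell sampling in at least 29 patients at 4–5 timepoints. Absolute lymphocyte count (ALC) is analysed in all treated patients (9.4.5), planned at 56.

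No formula for the cut, validation set or correction for a searched cut is given. The SAP text available for review contains no slope or kinetic biomarker analysis, so it does not close the gap.

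**The concern.** A threshold derived from a data set and then used to test a hypothesis in that same data set keeps its error rate only if the outcome played no part in choosing it. The protocol states that the cut is data-driven, so this is more than a missing detail. It says nothing about what may inform the choice. The trial is single-arm and open-label, and no step is described that would keep survival data from whoever sets the cut.

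At stake is how to read any kinetic marker that comes out of this substudy. A cut tuned to separate survival curves yields significant markers by chance and exaggerates their effect. A cut taken from the spread of the slopes does not. The two would look the same in a report.

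**Working it through.** **The plan's figure.** The only figure on this point is the 5% level, which is set and not derived. There is nothing to reproduce, so the false-positive rate was simulated.

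**Inputs from the protocol.** n = 29 (section 6.4.3, a minimum); 5% level, three slope groups, and PFS and OS as outcomes (section 9.4.5).

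**Assumptions, because the protocol is silent.** Two-sided log-rank test for the slope groups; normally distributed slopes unrelated to outcome; exponential event times; 0%, 20% or 35% of patients censored; smallest group allowed about 25%, 20% or 10% of patients (8, 6 or 3 of 29). Each setting had 3,000 to 5,000 runs, so the simulation standard error is below 1 percentage point.

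**Case A: the cut uses slope values only.** One endpoint, n = 29:

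- two groups split at the median: about 5–6%;
- three groups at the tertiles: about 6–8%;
- three groups at ±0.5 SD of the slopes: about 6–9%.

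The excess over 5% is mainly small-sample error of the three-group log-rank test. If a hit on either PFS or OS counts, the rates are 10–11% (median) and 13–15% (±0.5 SD).

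**Case B: the cut is the one with the best log-rank result.** The largest statistic over all allowed cuts is compared with the ordinary 5% critical value. One endpoint, n = 29:

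| Cut structure | Smallest group 25% | 20% | 10% |
|---|---|---|---|
| One cut, two groups | 22–26% | 28–32% | 41–46% |
| Three groups, one symmetric threshold ±c | 8–11% | 18–21% | 33–37% |
| Three groups, two free cuts | 21–24% | 41–45% | 80–87% |

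Allowing groups of only 2 or 1 patients raises the one-cut rate further, to 49% and 59% (20% censoring). If either PFS or OS counts, each with its own best cut, one cut gives 39–66% and the symmetric three-group version 17–56%.

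**Large-sample check of the one-cut row.** The Miller–Siegmund approximation is P ≈ φ(z)(z − 1/z) ln{[(1 − ε)/ε]²} + 4φ(z)/z, with z = 1.96, φ(z) = 0.0584 and ε the smallest group share. The second term is 4 × 0.0584/1.96 = 0.119, and φ(z)(z − 1/z) = 0.0584 × 1.450 = 0.0847.

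- ε = 0.25: 0.0847 × ln 9 + 0.119 = 0.186 + 0.119 = 0.305
- ε = 0.20: 0.0847 × ln 16 + 0.119 = 0.235 + 0.119 = 0.354
- ε = 0.10: 0.0847 × ln 81 + 0.119 = 0.372 + 0.119 = 0.492

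These lie somewhat above the simulated rates and rise in the same way.

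**Sample size.** At n = 56 with 20% censoring, one searched cut gives 30% (smallest group 20%) and 44% (10%). More patients than 29, or the ALC population, do not remove the problem.

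**Effect of the fix.** Slope as a continuous covariate, n = 29, no effect: false-positive rate about 6%, against 7.5% for tertile groups (no censoring). With a log hazard ratio of 0.5 per SD, assumed linear, power is about 65% against 46% without censoring, 60% against 42% with 20% censoring, and 52% against 36% with 35%.

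**The case against.** The strongest reply is that the sentence on the threshold closes a paragraph solely about kinetic profiles, whose stated purpose is to tell a trend from no change. On that reading, the behaviour of the series means the spread of the slopes, and Case A applies. This stands: it is at least as natural as the other reading, and under it there is almost no inflation.

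A reader might infer that the plan searches for the cut that best separates survival, so that the 5% level becomes some fixed, much higher rate. The protocol does not support that. It never says that PFS or OS guides the cut, and the Case B rates depend on group-size limits and a cut structure that it does not give. Nor is the analysis confined to 29 patients: 29 is a minimum for the serum and blood-cell panels, and ALC uses all treated patients.

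Two further replies stand in part. The test for slope groups is not named, so the link to PFS and OS rests on the general sentence about all analysed parameters and on the substudy aim in section 6.4.3. And the work is optional and exploratory; tissue and baseline markers need no slope cut.

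None of this supplies a rule that keeps outcome out of the choice. The protocol already treats the kinetic variables as continuous, but it then groups the slopes, so the remedy is only half present.

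**Conclusion.** The point holds in a conditional form. The protocol commits to a cut set after the whole series is seen, relates the parameters to PFS and OS in the same patients, and has no outcome-blind rule or correction.

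The consequence depends on something the text leaves open. With a cut from slope values alone, the rate is about 5–9% per endpoint. With an outcome-guided cut at n = 29, it is about 22–46% for one searched cut into two groups and one endpoint, and about 8–87% for searched three-group cuts. These figures assume a log-rank test, an inert marker and smallest groups of about 10–25%. It does not follow that every candidate from the substudy is indistinguishable from noise; that would need the outcome-guided reading, and it would concern the slope-grouped markers only.

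This is a minor point, worth correcting because the correction is cheap on either reading. The primary endpoint and the decision rule of 17 survivors among 56 patients are untouched.

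**What to change.** In Protocol section 9.4.5, replace the sentence on the threshold with two commitments:

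1. The slope of each serum or blood biomarker is related to PFS and OS as a continuous covariate in a Cox model.
2. If three groups are shown, the no-change band is defined from assay or baseline variability, fixed and documented before slopes are linked to outcome, and the groups are labelled descriptive.

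If the sponsor does want a cut chosen on outcome, its p-value should come from a maximally selected statistic or a permutation test that repeats the search.

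The cost is a sentence or two and no new data. If a marker-only threshold was always intended, the change simply records it. The downside is that the displayed groups may separate less sharply. The change deals only with how the cut is chosen; which patients have enough samples for a slope is a separate question.
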